#### **9.3.7.2 Medical History, Chest X-ray, ECGs and Physical Examination**

Medical history, chest x-ray, ECGs and physical examination data will be listed by subject. All medical history will be coded using the most current version of MedDRA. Changes in ECGs and physical examination will be described in the text of the final study report.

### **9.3.7.3 Clinical Laboratory and Vital Signs**

All clinical laboratory results and vital signs measurements, and their change from baseline, will be summarized by treatment and time point of collection.

A shift table describing out-of-normal range shifts will be provided for clinical laboratory results.

### **9.3.7.4 Previous and Concomitant Medication**

All previous and concomitant medication will be listed by subject. Prior and concomitant medications will be coded using the most current World Health Organization – Drug Dictionary (WHO-DD).

## **10 ETHICS AND REGULATORY REQUIREMENTS**

### **10.1 General Requirements for Study Conduct**

The Investigator or designee is responsible for ensuring that the study is conducted in accordance with the clinical protocol and is in full compliance with regulatory requirements; the basic principles outlined in 21 CFR Parts 50, 54, 56 and 312; ICH-guidelines for Good Clinical Practice as published in the Federal Register on May 9, 1997; and the Declaration of Helsinki.

The Investigator is also responsible for protecting the rights, safety and welfare of subjects under the Investigator's care and for the control of study device under investigation.

The Investigator(s) (and sub-Investigators) will provide the Sponsor with her/his/their up-to-date scientific Curriculum Vitae (signed and dated) prior to start of the study and when new site personnel are added once the study commences.

### **10.2 Regulatory and Institutional Review Board Approval/ Independent Ethics Committee**

Regulatory approval will be obtained from the appropriate regulatory authority prior to initiation of the study protocol.

The Investigator is responsible for obtaining IRB/IEC approval for the study protocol and the subject informed consent form. A copy of the dated approval letter from the IRB/IEC stating the study title, and/or study number must be provided to the Sponsor before the start of screening and release of supplies. A list of the names of the committee members will be obtained for the Sponsor's and Investigator's records.

### **10.3 Written Informed Consent**

The Investigator or designee will inform the subject of the nature, risks and purpose of the study. A written informed consent form will be provided to each subject describing the study information. The consent must be reviewed and approved by IRB/IEC before use in the study. Each volunteer must sign and date this form prior to their participation in the study. A signed original consent form for each subject will be kept on file at the clinical site. A copy of the signed consent will be provided to the subject.

### **10.4 Confidentiality**

The Investigator at each site and its designees, employees and agents involved with the study will comply with relevant state and federal laws relating to confidentiality, privacy and security of subject's health information. Confidential data may be disclosed to the Investigator and employees, sponsor, IRB/IEC, FDA or other authorized representatives during the course of the

study or when requested. Information will remain confidential and will not be used for any purpose other than the type of review requested.

## **10.5 Protocol Modification/Amendments**

Sponsor modifications made to the experimental design, study parameters, subject selection or any other content in the protocol will be communicated with a protocol amendment(s) to the Investigator and FDA for review and approval. All amendments will require IRB/IEC review and approval prior to implementation.

## **10.6 Direct Access to Source Data/Documents**

Investigator will permit trial-related monitoring, audits, IRB/IEC review and regulatory inspections by providing direct access to source data/documents.

## **11 DEFINITION OF END OF TRIAL**

### **11.1 End of Trial in a Member State**

End of trial in a Member State of the European Union is defined as the time at which it is deemed that a sufficient number of subjects have been recruited and completed the study as stated in the regulatory application (i.e., clinical trial application [CTA]) and ethics application in the Member State. Poor recruitment (recruiting less than the anticipated number in the CTA) by a Member State is not a reason for premature termination but is considered a normal conclusion to the study in that Member State.

### **11.2 End of Trial in All Other Participating Countries**

End of trial in all other participating countries is defined as last subject last visit (LSLV).

## 12 DATA MANAGEMENT

Data will be handled and processed according to CRO's SOPs, which are written based on the principles of GCP. At all times, appropriate backup copies of the database and related software files will be maintained and the information will be appropriately protected from unauthorized access.

The eCRF development will be based on the study protocol. All eCRF data, including laboratory data, will be included in an integrated database. At the end of the study when the database is deemed clean, the integrated database will be locked (, all data entry, quality control, database edits, medical coding, SAE reconciliation complete). The data will then be processed, evaluated, and stored in anonymous form in accordance with applicable data protection regulations.

eCRFs will be kept for each subject and will document all study data. The eCRFs must be completed for each subject to allow the progress and results of the study to be closely followed by the study monitor.

The study monitor or designee will review the eCRFs for completeness and accuracy via Source Document Verification. Study written ICFs and all study specific logs will be verified for completeness, accuracy and plausibility.

### 12.1 Coding of Adverse Events, Concomitant Medication, and Medical History

After data entry, the AEs and medical history will be coded according to the MedDRA®. Where required, concomitant medication will be coded according to the WHO-DD. The versions of MedDRA® and WHO-DD used in the study will be specified in the data management plan (DMP).

## **13 DOCUMENTATION AND ADMINISTRATIVE CONSIDERATIONS**

### **13.1 Recordkeeping**

All essential documents specific to the study (including study file, source documentation, copies of eCRF, etc.) should be retained by the Investigator until at least two years after the last approval of a marketing application in an ICH region and until there are no pending or contemplated marketing applications in an ICH region or at least 25 years have elapsed since completion of this clinical trial. These documents should be retained for a longer period if required by the applicable regulatory authority or if needed by the Sponsor.

Every reasonable effort should be made by the Investigator to retain records enabling the follow up of subjects who have received study medication. The Investigator should notify the Sponsor and obtain approval prior to destroying any material retained from the study.

### **13.2 Disclosure of Data**

The Investigator agrees not to disclose data from this study without the prior written approval of the Sponsor.

### **13.3 Publication Policy**

It is intended that the results of the study may be published as scientific literature. Results may also be used in submissions to regulatory authorities. The following conditions are to protect commercial confidential materials (patents, etc.), not to restrict publication.

All information concerning the product subsequently generated from this study (such as patent applications, formulae, manufacturing processes, basic scientific data, or formulation information supplied to the Investigator by the Sponsor and not previously published) is considered confidential by and shall remain the sole property of the Sponsor. The Investigator agrees not to use it for other purposes without the Sponsor's written consent.

It is understood by the Investigator that the Sponsor will use the information developed in this clinical study in connection with the development of PRA023 and, therefore, may be disclosed as required to other Sponsor Investigators or any appropriate international regulatory authorities. In order to allow for the use of information derived from this clinical study, the Investigator understands that he or she has an obligation to provide the Sponsor with complete test results and all data developed during this study.

Prior to submitting the results of this study for publication or presentation, the Investigator will allow the Sponsor 60 days in which to review and comment upon the publication manuscript. In accordance with generally recognized principles of scientific collaboration, co authorship with any Sponsor personnel will be discussed and mutually agreed upon before submission of a manuscript to a publisher. The publication of study data may not be performed without the written prior approval of the Sponsor, and this approval shall not be unreasonably withheld.

During the period for review of a proposed publication from the Investigator, the Sponsor shall be entitled to make a reasoned request to the Investigator that publication be delayed for a period of up to 6 months from the date of first submission to the Sponsor in order to enable the Sponsor to take steps to protect its proprietary information, and the Investigator shall not unreasonably withhold consent to such a request. Any intended joint publication must precede any proposed individual publication.

## 14 QUALITY CONTROL AND QUALITY ASSURANCE

The study monitor will maintain a close liaison with the investigational site to clarify any problems that may arise, and to ensure that the Investigator is following the protocol. This liaison may consist of personal visits before the study is initiated and at appropriate intervals during the study and will include communications via telephone, facsimile, email, and letter. During site monitoring visits, information recorded on the eCRFs will be verified against source documents.

The Investigator agrees that Prometheus, its employees or agents, and regulatory health authorities will have the right from time to time, both during and after the course of this study, to audit and review medical records relating to this study.

A statement will be obtained from each subject participating in the study permitting the release of his/her medical records as necessary for inspection by authorized personnel of Prometheus, the FDA, and/or other regulatory health authorities.

## 16 APPENDIX

### 16.1 Modified Mayo Scoring System for Assessment of Ulcerative Colitis Activity

The Modified Mayo score ranges from 0 to 12, with higher scores indicating more severe disease. Data are from Schroeder et al. (Schroeder 1987).

#### Stool frequency†

- 0 = Normal no. of stools for this subject
  - 1 = 1 to 2 stools more than normal
  - 2 = 3 to 4 stools more than normal
  - 3 = 5 or more stools more than normal
- Subscore, 0 to 3

#### Rectal bleeding‡

- 0 = no blood
  - 1 = visible blood with stool less than half of the time
  - 2 = visible blood with stool half of the time or more
  - 3 = passing blood alone
- Subscore, 0 to 3

#### Findings on endoscopy:

- 0 = Normal or inactive disease
  - 1 = Mild disease\* (erythema, decreased vascular pattern)
  - 2 = Moderate disease (marked erythema, lack of vascular pattern, friability, erosions)
  - 3 = Severe disease (spontaneous bleeding, ulceration)
- Subscore, 0 to 3

#### Physician's global assessment§

- 0 = Normal
  - 1 = Mild disease
  - 2 = Moderate disease
  - 3 = Severe disease
- Subscore, 0 to 3

† Each subject serves as his or her own control to establish the degree of abnormality of the stool frequency.

‡ The daily bleeding score represents the most severe bleeding of the day.

§ The physician's global assessment acknowledges the three other criteria, the subject's daily recollection of abdominal discomfort and general sense of wellbeing, and other observations, such as physical findings and the subject's performance status.

\* Modified Mayo score considers mild disease (endoscopy score of 1) to be without any friability.

### **16.1.1 Partial Mayo Scoring System for Assessment of Ulcerative Colitis Activity**

For calculation of Partial Mayo score, the mucosal appearance on endoscopy (i.e., findings on endoscopy component of Mayo score) is not included.

### **16.1.2 3-Component Modified Mayo Score**

For calculation of the 3-component Modified Mayo Score, the physician's global assessment component of Mayo score is not included.

1 INTRODUCTION

This statistical analysis plan (SAP) addendum describes the additions or modifications to the approved SAP V01 dated 10 August 2022 and is based on the study protocol version 4.0.

The SAP addendum covers the following topics of statistical analyses of the Induction Period for Cohort 1 following the corresponding database lock:

- Modification of Section 6.10, for the approach to multiplicity adjustment.
- Addition of an interim analysis for subjects with CDx+ based on protocol specified algorithm and the alternative algorithms.

2 MODIFICATION TO APPROACH FOR MULTIPLICITY

The following text will replace the content of Section 6.10 of the SAP V01.

A closed hierarchical procedure will be used to control for multiple comparisons of primary and key secondary endpoints. The order of testing will be primary endpoint, followed by the key secondary endpoints in the order as displayed in [Table 1](#). If at any point in this sequential procedure the null hypothesis is not rejected, the testing procedure will be terminated. All subsequent analyses would be considered exploratory.

The primary endpoint will be analyzed and compared between PRA023 and placebo treatment groups in FAS from Cohort 1. The primary endpoint, the proportion of subjects achieving clinical remission, will be tested between the 2 treatment groups at 1-sided significance level of 0.025 using CMH. If significant, the secondary endpoints will be tested sequentially between the 2 treatment groups at significance level indicated in the table.

Table 1 Primary and Key Secondary Endpoints in Cohort 1

Endpoints	Analysis Population (1-sided alpha)
Primary	
Proportion of subjects in 3-component Modified Mayo Score clinical remission (as defined by endoscopic subscore of 0 or 1, rectal bleeding subscore of 0, and stool frequency subscore of 0 or 1 and not greater than Baseline) at Week 12	FAS (0.025)
Secondary	

 • Proportion of subjects with endoscopic improvement (as defined by endoscopy subscore ≤ 1 with no friability) at Week 12 	FAS (0.025)

 • Proportion of subjects in 3-component Modified Mayo Score clinical response (as defined by a reduction from Baseline ≥ 2 points and $\geq 30\%$ in 3-component Modified Mayo Score, accompanied by a reduction ≥ 1 in rectal bleeding subscore or absolute rectal bleeding subscore ≤ 1) at Week 12 	FAS (0.025)

	<h2>Statistical Analysis Plan - Addendum</h2>
---	---

Version: 01

Status: Final

Endpoints	Analysis Population (1-sided alpha)

 Proportion of subjects with symptomatic remission (as defined by stool frequency (SF) subscore = 0 and rectal bleeding (RB) subscore = 0) at Week 12 	FAS (0.025)

 Proportion of subjects with histologic-endoscopic mucosal healing (defined as Geboes score \leq 2B.1 and endoscopy subscore \leq 1 with no friability) at Week 12 	Histology Analysis Set (0.025)

 Proportion of subjects with histologic improvement (defined as Geboes score \leq 3.1) at Week 12 	Histology Analysis Set (0.025)

 Proportion of subjects with histologic-endoscopic mucosal improvement (defined as Geboes score \leq 3.1 and endoscopy subscore \leq 1 with no friability) at Week 12 	Histology Analysis Set (0.025)

 Proportion of subjects with IBDQ response, as defined by \geq 16-point increase from Baseline at Week 12 	FAS (0.025)

 Proportion of subjects in 3-component Modified Mayo Score clinical remission at Week 12 in CDx+ subjects (Cohort 1 + Cohort 2) 	CDx+ FAS (0.0245)

 Proportion of subjects with endoscopic improvement, as defined by endoscopy subscore \leq 1 with no friability) at Week 12 in CDx+ subjects (Cohort 1 + Cohort 2) 	CDx+ FAS (0.0245)

 Proportion of subjects in 3-component Modified Mayo Score clinical response at Week 12 in CDx+ subjects (Cohort 1 + Cohort 2) 	CDx+ FAS (0.0245)

 Proportion of subjects with symptomatic remission (as defined by rectal bleeding score = 0 and stool frequency score = 0) at Week 12 in CDx+ subjects (Cohort 1 + Cohort 2) 	CDx+ FAS (0.0245)

 Proportion of subjects with histologic-endoscopic mucosal healing (defined as Geboes score \leq 2B.1 and endoscopy subscore \leq 1 with no friability) at Week 12 in CDx+ subjects (Cohort 1 + Cohort 2) 	CDx+ Histology Analysis Set (0.0245)

 Proportion of subjects with histologic improvement (defined as Geboes score \leq 3.1) at Week 12 in CDx+ subjects (Cohort 1 + Cohort 2) 	CDx+ Histology Analysis Set (0.0245)

 Proportion of subjects with histologic-endoscopic mucosal improvement (defined as Geboes score \leq 3.1 and endoscopy subscore \leq 1 with no friability) at Week 12 in CDx+ subjects (Cohort 1 + Cohort 2) 	CDx+ Histology Analysis Set (0.0245)

 Proportion of subjects with IBDQ response, as defined by \geq 16-point increase from Baseline at Week 12 in CDx+ subjects (Cohort 1 + Cohort 2) 	CDx+ FAS (0.0245)

The alpha reduction by 0.001 (2-sided) is due to the added Sponsor unblinded interim analysis of CDx+ population based on Cohort 1. This analysis of the CDx based on Cohort 1 is considered interim because data from Cohort 1 CDx+ subjects are considered interim results of CDx+ FAS (Cohort 1 + Cohort 2). While [Section 3](#) of this addendum will detail the analyses, the interim analysis intends to estimate the effect size of PRA023 comparing to the placebo in CDx+ subjects. A minimal alpha level is allocated to the interim analysis, as no efficacy early stopping is expected.

3 ANALYSIS OF CDx+ SUBPOPULATIONS IN COHORT 1

3.1 DEFAULT CDx+

The protocol specified CDx status, called default UC algorithm, was used for stratification of the randomization in Cohort 1. As designed, CDx+ subjects will be enrolled in Cohort 2 following the completion of Cohort 1 enrollment. The analysis for CDx+ related secondary endpoints will be analyzed when all subjects in Cohort 2 complete Week 12 or early discontinue. The combined CDx+ subjects across Cohort 1 and Cohort 2 will constitute the CDx+ FAS for these secondary endpoints.

At the time of this SAP addendum, the planned interim analysis when approximately 80% of subjects in Cohort 1 (i.e., ~96 subjects) have reached Week 12 or early terminated from the study has been completed. DMC reviewed the unblinded interim efficacy and safety data for all available subjects and CDx+ subjects on 19 October 2022. Following the review, DMC recommended to continue the enrollment of Cohort 2, and informed a total sample size of 48 for the cohort.

Based on the emerging information related to CDx development and validation, the Sponsor has made the decision to conduct an additional analysis for CDx+ subpopulation based on Cohort 1 data to assess the effect size of PRA023 in CDx+ subjects. In addition to the subgroup analysis based on CDx status for the primary endpoint, [Table 2](#) lists endpoints that will be assessed for the Cohort 1 CDx+ subpopulation. The methods of analysis are similar to those specified in SAP V01, with the following exceptions:

- The analysis sets are defined as CDx+ subjects who are randomized and treated in Cohort 1.
- No statistical hypothesis testing will be performed between PRA023 and Placebo treatment groups, while 95% confidence intervals will be presented for the estimation of treatment difference.

Table 2 Analyses for CDx+ Population in Cohort 1

Endpoints	Treatment Difference
Proportion of subjects in 3-component Modified Mayo Score clinical remission at Week 12	Included in subgroup analysis of the primary endpoint
Proportion of subjects with endoscopic improvement, as defined by endoscopy subscore ≤ 1 with no friability) at Week 12	Risk difference and 95% CI
Proportion of subjects in 3-component Modified Mayo Score clinical response at Week 12	Risk difference and 95% CI
Mean change in Partial Mayo Score over time Mean change in PRO-2 Score over time	Difference of LS mean and 95% CI
Fold change in hsCRP over time Fold change in fecal calprotectin over time	Ratio of geometric means and 95% CI

3.2 CDx+ BASED ON ALTERNATIVE ALGORITHMS

To evaluate whether a CDx call can render a different treatment effect of PRA023 comparing to placebo, alternative algorithms (Table 3) will also be assessed.

Table 3 Alternative CDx Algorithms

Algorithm Name	Description
entrocyte.RDS	Score and predicted label (high/low) based on Ileum-derived entrocytes from subject's germline genetics
colon.bma.model.cluster Resident.macrophages.RDS	Score and predicted label (high/low) based on Colon-derived resident macrophages from subject's germline genetics
colon.bma.model.cluster.TA.RDS	Score and predicted label (high/low) based on Colon-derived Transit-Amplifying (TA) cells from subject's germline genetics
colon.bma.model.cluster.Goblet.cell.RDS	Score and predicted label (high/low) based on Colon-derived Goblet cells from subject's germline genetics
modc.RDS	Score and predicted label (high/low) based on Ileum-derived monocyte-derived dendritic cells (moDC) from subject's germline genetics

For each CDx+ call, descriptive statistics for the endpoints listed in Table 2 will be provided by treatment group. Additionally, the point estimate and multiplicity controlled 95% CI for the treatment difference in clinical remission at Week 12 will be plotted against the estimated overall treatment effect in Cohort 1. Given the number of alternative CDx algorithms to be evaluated, the conventional confidence intervals are subject to an inflation of the alpha. A re-sampling based method [1] will be used to construct the 95% CI for each CDx+ call subpopulation with an overall alpha level of 0.05 (2-sided) across alternative algorithms.

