### 8.2 Justification of Sample Size

The study is planned to randomize up to approximately 170 subjects, approximately 120 in Cohort 1 and up to 50 in Cohort 2. A sample size of 60 per arm in Cohort 1 will enable a statistical power of > 80% for the primary endpoint at 1-sided significance level of 0.025 using Cochran-Mantel-Haenszel (CMH), assuming clinical remission rate of 5% for placebo and 24% for PRA023. Additionally, the sample size will confer > 80% power to achieve statistical significance for the 1st secondary endpoint of endoscopic improvement with an overall 1-sided alpha level of 0.025, assuming the endoscopic improvement rates are 15% and 38% for placebo and PRA023 groups, respectively.

Additionally, for analyses of the CDx+ population (combining CDx+ subjects from Cohort 1 and Cohort 2), a sample size of 40 per arm will provide a statistical power of  $\geq 80\%$  at a 1-sided alpha level of 0.025, according to a group sequential design with a non-binding futility interim analysis when approximately 18 subjects are anticipated per arm reach Week 12, assuming clinical remission rate of 5% for placebo and 31% for PRA023.

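### The alternative-CDx plot sets the CDx+ interval against an overall estimate that contains the same subjects; for that comparison the bars are too wide, and a CDx+ minus CDx- contrast should be added

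*SAP*

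**What the plan says.** The first sentence of SAP addendum 3.2 gives the purpose: "To evaluate whether a CDx call can render a different treatment effect of PRA023 comparing to placebo". Table 3 there lists five alternative algorithms. For each CDx+ call the plan provides descriptive statistics by treatment group, plus one interval: a "multiplicity controlled 95% CI for the treatment difference in clinical remission at Week 12 will be plotted against the estimated overall treatment effect". The reference is taken from the whole of Cohort 1. The intervals come from a re-sampling method "with an overall alpha level of 0.05 (2-sided) across alternative algorithms".

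Section 3.1, written for the default CDx call, fixes the population ("The analysis sets are defined as CDx+ subjects who are randomized and treated in Cohort 1") and the inferential status: "No statistical hypothesis testing will be performed between PRA023 and Placebo treatment groups, while 95% confidence intervals will be presented". Section 2 of the addendum describes the Cohort 1 CDx+ analysis as an estimate of the PRA023 effect size in CDx+ subjects.

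The supplied documents plan no CDx- result, no CDx+ minus CDx- contrast and no interval for CDx+ minus overall for any alternative algorithm. SAP V01 is not among them.

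**The concern.** Whether a call gives a different effect is a question about effect modification. The planned interval describes uncertainty about one subgroup's effect. The reference it is set against is not independent, because the CDx+ subjects contribute to the overall Cohort 1 estimate. The two move together, so the gap between them is less variable than the CDx+ bar suggests. The gap is also only a fraction of the CDx+ versus CDx- difference, and that fraction changes with the share called positive. Five algorithms on one plot are then read on different scales.

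At stake is the reading of the candidate algorithms. Section 3.2 is the only analysis in the supplied documents that evaluates them. Protocol Sections 2.2 and 3.2 carry a secondary objective and endpoint for clinical remission in subjects who are CDx+ by an alternative algorithm. The documents do not say how that algorithm is chosen.

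**Working it through.** **Inputs.** Cohort 1 has 60 per arm (Protocol 8.2: "A sample size of 60 per arm in Cohort 1 will enable a statistical power"). Protocol 8.2 assumes remission of 5% on placebo, 24% on PRA023 overall and 31% on PRA023 in CDx+. For the default call the interim expects "approximately 18 subjects are anticipated per arm reach Week 12", out of about 96/2 = 48 per arm, so p = 18/48 = 37.5%. Alternatively, 80 CDx+ subjects in total (40 per arm) less the 48 in Cohort 2 (SAP addendum 3.1) leaves 32/120 = 27% in Cohort 1. No share is given for any alternative algorithm, so I assume 25-60%.

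**The plan's own figures.** A two-proportion test with 60 per arm, 5% against 24%, one-sided 0.025, has power 0.849, consistent with the stated > 80%. The information fraction 18/40 = 0.45 also matches. The plan states no figure for the width of these intervals.

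**Width.** Let D+ and D- be the risk differences in CDx+ and CDx-, and D = pD+ + (1-p)D- the overall one.

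- Gap shown: D+ - D = (1-p)(D+ - D-).
- With equal per-subject variance, Var(D+) = V/p and Var(D-) = V/(1-p), so Var(D+ - D) = (1-p)V/p = (1-p)Var(D+).
- Plotted SE over correct SE = 1/sqrt(1-p).

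| p | 1/sqrt(1-p) | Excess, equal variance | Excess, protocol rates |
|---|---|---|---|
| 25% | 1.155 | 15% | 18% |
| 37.5% | 1.265 | 26% | 32% |
| 50% | 1.414 | 41% | 52% |
| 60% | 1.581 | 58% | 79% |

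At the default call's 27% the equal-variance excess is 17%. Simulation of 200,000 trials under a uniform effect gave ratios of 1.156, 1.259 and 1.581 at 25%, 37.5% and 60%.

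**Worked case, protocol rates, p = 37.5%** (22.5 CDx+ and 37.5 CDx- per arm):

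- PRA023 rate in CDx-: (0.24 - 0.375 × 0.31)/0.625 = 0.198.
- SE(D+) = sqrt[(0.05 × 0.95 + 0.31 × 0.69)/22.5] = 0.108.
- SE(D-) = sqrt[(0.05 × 0.95 + 0.198 × 0.802)/37.5] = 0.074.
- SE(D+ - D-) = 0.131, so SE(D+ - D) = 0.625 × 0.131 = 0.082. The ratio is 1.32.
- Unadjusted half-width: about 21 points as plotted, against about 16 points for the gap. The true gap is 0.26 - 0.19 = 7 points.

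**How often the bar would exclude the overall value.** The SAP sets no such rule; this only measures how much evidence the plot conveys. The direct contrast and a correct interval for the gap give the same z, because estimate and SE both scale by (1-p).

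- Uniform effect, unadjusted 95% bar: 2[1 - Φ(1.96/sqrt(1-p))] = 2.4%, 1.3% and 0.2% at p = 25%, 37.5% and 60%. The display is conservative, increasingly so as p rises.
- Protocol rates, p = 37.5%: planned bar 1 - Φ((0.211 - 0.070)/0.082) ≈ 4%; direct contrast about 14%. Simulation gives about 5% and 14%. At a critical value of 2.5 (five correlated intervals need about 2.44-2.57) the figures are about 1% and 6%.
- Large assumed marker effect, 40 points in CDx+ and 5 in CDx-, placebo 5%, p = 37.5%: simulation gives about 50% as planned and 77% for the direct contrast, and 24% against 59% at 2.5.

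**The case against.** The strongest reply is that the bars fit a stated aim. Section 2 of the addendum wants the effect size in CDx+, Section 3.1 is estimation without testing, and the protocol's alternative-algorithm endpoint is itself PRA023 against placebo within CDx+. For that quantity the width is correct. This stands, and the CDx+ intervals should stay. It does not answer Section 3.2's own opening question, which concerns a difference in effect.

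It is also fair that the plot is descriptive, affects no primary or key secondary test, and does not raise the false-positive rate.

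A reader might infer three stronger things that the documents do not support:

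- **That algorithms are accepted or rejected by whether the bar crosses the overall line.** Section 3.2 states no such rule, and it does not say that the overall estimate is drawn without its own interval.
- **That a real marker effect will be missed because of this display.** With a large effect the planned bar still excludes the overall value about half the time. At the protocol's own rates the direct contrast would usually miss the effect too.
- **That the plot favours algorithms calling few subjects positive.** For a fixed marker effect and equal variances the plotted z is proportional to (1-p)·sqrt(p), which peaks at p = 1/3. In the 40-against-5-point case the bar excludes the overall value about 33% of the time at p = 10%, 50% at 37.5% and 24% at 60%. Only the loss relative to the direct contrast grows steadily with p.

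**Conclusion.** The concern holds in a limited form. Section 3.2 asks about a difference in effect but plans no interval for one. The CDx+ bars are valid for the effect within CDx+, and too wide by about 1/sqrt(1-p) when read against the overall effect. Evidence of a marker effect is therefore understated, and by different amounts for algorithms with different positive shares.

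The size depends on assumptions. The range p = 25-60% is mine, since the documents support only about 27-37.5%, and only for the default call. The lower set of excess widths assumes equal variances; the higher set uses the protocol's rates. The frequencies are for unadjusted intervals unless stated. SAP V01 could contain relevant subgroup methods that cannot be seen here. With about 120 subjects, evidence on effect modification will be weak whichever interval is shown; the change makes the display answer its own question but does not make the study well powered for it.

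**What to change.** In SAP addendum 3.2:

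1. Keep the CDx+ point estimates and simultaneous intervals, labelled as effects within CDx+.
2. For each algorithm, show the CDx- effect and the number called positive and negative in each arm beside the CDx+ effect.
3. Add, for each algorithm, (PRA023 minus placebo in CDx+) minus (PRA023 minus placebo in CDx-), with simultaneous 95% intervals across the five contrasts from the same re-sampling method, plotted against zero.
4. State that these contrasts are estimates and that no decision rule is attached, or state the rule if there is one.

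The cost is a short text change and a little more programming; no new data are needed. The contrast interval will be wider in absolute points than the CDx+ interval: at p = 37.5% with the protocol's rates, SE 0.131 against 0.108, about 21% wider. That is the actual uncertainty about a difference in effect.
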